### **7.8.2      Laboratory data**

The analyses of laboratory data will be descriptive in nature and will be based on BI standards [BI-KMED-BDS-HTG-0042] ([10](#)).

Laboratory data will be analysed qualitatively via comparison of laboratory data to their reference ranges. Values outside the reference range as well as values defined as possibly clinically significant will be flagged in the data listings.

Clinically relevant findings in laboratory data will be reported as baseline conditions (at screening) or as adverse events (during the trial) if judged clinically relevant by the investigator, and will be analysed as such.

It is the investigator's responsibility to decide whether a lab value is clinically significantly abnormal or not (at the RPM/DBLM at the latest).

Descriptive statistics of laboratory data (normalised values) including change from baseline will be calculated by time point based on the worst value of the patient at that time point (or assigned to that planned time point).

### **7.8.3      Vital signs**

For vital signs (blood pressure, pulse rate and body weight), descriptive statistics including change from baseline will be calculated by treatment group and by planned time point based on the first value of the patient at that planned time point (or assigned to that planned time point). In the listing the difference from baseline will also be displayed.

Clinically relevant findings in vital signs will be reported as AEs.

### **7.8.4      ECG**

#### **Continuous safety ECG monitoring (by investigator)**

Clinically relevant abnormal findings will be reported as adverse events.

No separate listing or analysis of continuous ECG monitoring will be prepared.

#### **12-lead ECG**

Abnormal findings will be reported as baseline conditions (at screening) or as AEs (during the trial) if judged clinically relevant by the investigator.

All evaluations of ECG data will be based on the TS.

### **Listing of individual data**

For all quantitative endpoints, listings of individual data will be shown in Appendix 16.2. For QTcB and RR only listings will be provided. Occurrences of notable findings will be flagged.

Comments regarding the ECGs will be listed.

### **Categorical endpoints**

For the categorical endpoints frequency tables will be provided.

Categorical endpoints will also include morphological findings that might be attributable to treatment. In particular, new onsets of findings not present at baseline will be explored. A morphological finding observed on treatment that was not reported at baseline will be categorized as a 'new onset' of this finding.

For all patients with any notable finding in ECG intervals, a separate listing will be created as end-of-text display (based on the same display template as in Appendix 16.2), and the corresponding time profiles will be shown.

### **Quantitative endpoints**

Descriptive statistics (N, mean, SD, min, median, max) will be provided for the absolute values and changes from baseline over time of QTcF, QT, HR, PR and QRS. The time profiles of mean and SD for the changes from baseline on treatment will be displayed graphically by treatment.

## **7.8.5 Others**

### **Physical examination**

Physical examination findings, including general appearance, neck, lungs, cardiovascular system, abdomen, extremities, and skin will be reported as relevant medical history/baseline condition (i.e., a condition already existent before intake of study drug) or as AE and will be summarised as such.

No separate listing or analysis of physical examination findings will be prepared.

### **Ophthalmological data**

The following endpoint will be listed and will be analysed descriptively by treatment group (SRD and MD part) and in total (SRD part only):

- The results of the IOP measurements as well as the corresponding changes from baseline for each time point and the study eye / fellow eye

All of the following endpoints will be listed only (for the study eye / fellow eye):

- The results of the SUN grading for Anterior Chamber Cells (slit lamp)

- Other results of the Slit Lamp examination / Indirect ophthalmoscopy (categories defined in eCRF) regarding eyelid, conjunctiva, cornea, anterior chamber cells, anterior chamber flare, hypopyon, iris, lens status, lens opacity, posterior capsule status, vitreous chamber cells, vitreous chamber flare, posterior vitreous detachment, optic disc, cup to disc ratio, central retina, retinal periphery, retinal tear, retinal detachment).
- Color fundus photography (evidence of GA (*present, absent, cannot determine*), GA distribution (*single lesion, multifocal, cannot determine*), GA Foveal Involvement (*minimal, moderate, complete, cannot determine*), choroidal neovascular membrane (*yes, no, cannot determine*), drusen (*present, absent, cannot determine*), reticular pseudo drusen (*present, absent, cannot determine*), intraretinal hemorrhage (*yes, no, cannot determine*), subretinal hemorrhage (*yes, no, cannot determine*), CFP additional findings, additionally for MD part: hemorrhage (*yes, no, cannot determine*), optic disc pallor (*yes, no, q, cannot determine*), cup to disc ratio (%), optic disc margin (*well defined, ill defined, cannot determine*))
- Categorical assessments from OCT (overall quality (*good, fair, poor*), volume (uL), geographic atrophy (*yes, no*), GA foveal involvement (*no GA, minimal or no, moderate, complete, cannot determine*), drusen (*yes, no*), hyper reflective drusen spots (*no drusen, yes, no*), subretinal drusen deposits (*yes, no*), choroidal neovascular membrane (*yes, no*), intraretinal fluid (*yes, no*), outer retinal tabulation (*yes, no*), ellipsoid zone disruption (*yes, no, cannot determine*), disruption compare to previsit (*no EZ disruption outside GA, progressed, regressed, no change, newly observed*), granularity (*yes, no, cannot determine*), granularity compare to previsit (*no os granularity outside GA, progressed, regressed, no change, newly observed*), correct segmentation lines (*yes, no*), segmentation lines were off level (*no off lines, mild, moderate, severe*), other findings, additionally for MD part: evidence of optic disc swelling (*yes, no, cannot determine*), retinal nerve fiber layer total volume, retinal nerve fiber layer superior temporal, retinal nerve fiber layer temporal, retinal nerve fiber layer inferior temporal, retinal nerve fiber layer inferior nasal, retinal nerve fiber layer nasal, retinal nerve fiber layer superior nasal, )
- Categorical and other assessments from OCT-A (presence of CNV neovascularisation (*yes, no*), location of CNV (*no CNV, involving foveal center, subfoveal but not involving foveal center, extrafoveal*), additional findings)
- Categorical assessments from FAF (definitely decreased autofluorescence AR (*present, absent*), lesion distribution (*DDAF absent, single lesion, multifocal*), foveal region involvement in DDAF (*DDAF absent, no involvement, minor, moderate, major involvement*), junctional zone pattern (*DDAF absent, focal banded, patchy, diffuse trickling, diffuse reticular, other diffuse pattern, no increased AF, CD*), background autofluorescence (*normal, homogenously increased, homogenously decreased, reticular pseudo-drusen, other*), que. decreased autofluorescence (*present, absent*), QDAF present (*QDAF absent, surrounding areas of DDAF, isolated from areas of DDAF, both, no DDAF areas*), other findings)

**8. TIMEPOINT OF RELEASE OF TREATMENT  
INFORMATION**

The treatment information will be loaded into the trial database after completion of enrolment.

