### 3.2 DISCUSSION OF TRIAL DESIGN, INCLUDING THE CHOICE OF CONTROL GROUP(S)

This trial is designed to establish a safe and tolerable dose for further testing in phase II trials. The trial consists of separate SRD and MD parts. A comparison between the untreated versus the treated eye is considered adequate to derive a safe and tolerable dose and therefore neither parts of this trial will use a comparison to sham injection.

The SRD dose escalation is designed to avoid exposure of too many patients to subtherapeutic doses while on the other hand the goal of safety and rapid dose finding is preserved.

The dose escalation and cohort size will be decided by the SMC, guided by a BLRM with overdose control. An EWOC design will increase the chance of treating patients at efficacious doses while reducing the risk of overdosing. The use of Bayesian models for Phase I studies has also been advocated by the European Medicines Agency (EMA) guideline on small populations [[R07-4856](#)] and by the Food and Drug Administration (FDA) [[R13-4881](#)].

One MD cohort (3 injections in a 4-weekly interval) will be included after the SRD part. This part of the trial will generate additional safety data and plasma concentrations of BI 754132 after MD. These data will further support the definition of the injection frequency in later studies.

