### 6.2 DETAILS OF TRIAL PROCEDURES AT SELECTED VISITS

Study procedures and assessments to be performed at each visit are listed in [Flow Chart I](#) and [Flow Chart II](#), and in [Appendix 10.3](#). Additional details regarding visit procedures are provided below.

All ophthalmic examinations will be performed in both eyes and should be performed in specific order described below.

Before pupil dilation: BCVA assessment, slit lamp examination, ERG and ocular tonometry (for determination of IOP).

After dilation: slit lamp examination, SD-OCT, OCT-A, colour fundus photography, fundus autofluorescence angiography. For the SRD part, IOP can be repeated after pupil dilation and after IVT injection on discretion of the investigator. For the MD part, IOP must be taken before pupil dilation and then repeated 30 to 50 min after IVT injection at Visit 2, 3 and 4.

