## 6.7 BASELINE, TIME WINDOWS AND CALCULATED VISITS

The baseline value for laboratory data, vital signs data and ophthalmological data is defined as the last measurement before first administration of BI 754132 (= value at V2, in case no actual time is given in data).

**Section 5.2.4 of the CTP:** *For the endpoints, baseline is defined as the value at Visit 2; if not measured at Visit 2 then baseline is the value at Visit 1.*

The acceptable time windows for visits are given in the CTP Flow Charts.

Adherence to time windows will be checked via the consistency check listings at the RPM/DBLM.

Unscheduled measurements of laboratory data, ophthalmologic data and vital signs data will be assumed to be repeat measurements of the most recent scheduled measurement (e.g. for follow-up or confirmation of a particular value). Therefore, unscheduled measurements will be assigned to the planned time point of the previous scheduled measurement.

**Section 5.2.6 of the CTP:** *Central ECG lab evaluation will be performed for all ECGs indicated in the CTP Flow Charts. For all ECGs, this will include the intervals RR, PR, QRS and QT measured semi-automatically. The screening ECGs will be checked for abnormalities. [...].*

At Visit 1, single ECGs will be recorded. At Visit 2-10, triple ECGs will be recorded (three single ECGs within 180 sec).

**Section 7.2.5 of the CTP:** *The baseline value of an ECG variable is defined as the mean of the ECG measurements prior to drug administration on visit 2. The screening ECGs will not be included in calculation of baseline.*

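### The SAP's IOP baseline rule ignores pupil state, so an optional post-dilation reading taken before the SRD injection can replace the scheduled pre-dilation reading as baseline

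*SAP*

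**What the plan says.** **Baseline.** SAP 6.7 states: "The baseline value for laboratory data, vital signs data and ophthalmological data is defined as the last measurement before first administration of BI 754132". A parenthesis adds that this is the "value at V2, in case no actual time is given in data". The same section repeats Protocol 5.2.4, where "baseline is defined as the value at Visit 2; if not measured at Visit 2 then baseline is the value at Visit 1". None of these statements mentions pupil state or separates a scheduled reading from a repeat.

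**When IOP is measured.** Protocol 6.2 and Flow Chart I (footnote 8) place tonometry before dilation. Section 6.2 then adds: "For the SRD part, IOP can be repeated after pupil dilation and after IVT injection on discretion of the investigator". In the multiple dosing (MD) part the pre-dilation reading is mandatory, and the only repeat provided for is the one 30 to 50 minutes after injection.

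**Order at the dosing visit.** Under Protocol 6.2.1.2 the SRD injection comes after the Visit 2 ophthalmological assessments, which include imaging through a dilated pupil.

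**What is reported.** SAP 7.8.5 gives listings and descriptive statistics for "The results of the IOP measurements as well as the corresponding changes from baseline for each time point", by treatment group and, in the SRD part, in total.

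**Which value counts.** SAP 7.8.2 uses the worst value at a time point for laboratory data, and SAP 7.8.3 uses the first value for vital signs. The readable SAP has no such rule for IOP, although SAP 6.7 files unscheduled ophthalmological readings under the preceding scheduled time point.

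**The concern.** A change from baseline can be interpreted only if both readings were taken under the same conditions. The protocol fixes that condition for scheduled IOP and then allows SRD readings under a different one. The SAP rule chooses the baseline by time alone. It therefore prefers a later dilated reading to the earlier scheduled one whenever both precede the injection.

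A displaced baseline carries into that patient's change at every later visit. The planned SRD groups have 3 patients, with 6 at the final dose, so one patient moves the group mean noticeably. Whether a repeat is taken is the decision of an investigator in an open-label trial, so the affected patients would not be a random subset.

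Because the SAP has no selection rule, the follow-up side of the change is not fixed either. By the current protocol version all 15 SRD patients had completed, and the SAP is dated later. A choice left unwritten would be made by people who can see the values.

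**Working it through.** The plan gives no figure on this point to reproduce. The check applies SAP 6.7 to the readings that the protocol allows, and then works out the effect on a group mean.

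**Step 1. Which reading becomes the baseline?**

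| Situation at Visit 2 | Baseline under SAP 6.7 |
|---|---|
| SRD, no post-dilation repeat before injection | Scheduled pre-dilation reading |
| SRD, post-dilation repeat before injection, clock times recorded | The dilated repeat, because it is the last pre-dose reading |
| SRD, same repeat, no clock times | Not determined: Visit 2 holds two pre-dose values |
| MD | Pre-dilation reading; the only repeat provided for is after injection |

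**Step 2. Effect on one patient.** Let d be the dilated minus the undilated reading in the same eye, taken as constant over visits. The error in change (follow-up minus baseline), compared with both readings undilated, is:

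| Baseline | Follow-up | Error |
|---|---|---|
| undilated | undilated | 0 |
| dilated | undilated | −d at every such visit |
| undilated | dilated repeat | +d at that visit only |
| dilated | dilated repeat | 0 |

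The third and fourth rows are possible because the SRD permission is attached to the whole IOP row of Flow Chart I, and the SAP does not say which reading is used.

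**Step 3. Effect on the group mean.** With k of n patients having a dilated baseline and undilated follow-up, the mean change shifts by k·d/n in absolute size. The documents give no d; 1 to 5 mmHg is an assumption used to show scale. For k = 1:

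- n = 3: 1/3 = 0.33 to 5/3 = 1.67 mmHg
- n = 6: 1/6 = 0.17 to 5/6 = 0.83 mmHg
- SRD total, n = 15: 1/15 = 0.07 to 5/15 = 0.33 mmHg

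If every patient in a group were affected (k = n), the shift would be d itself.

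**Step 4. What does not depend on this baseline?** The IOP criterion for a dose limiting event (Protocol 5.2.1, SAP 7.4) is an absolute level, over 30 mmHg for 3 days. The SRD primary endpoint and the dose-escalation model fitted to these events therefore do not use the IOP baseline.

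**The case against.** **The repeat is hypothetical.** No text reports a dilated reading before an SRD injection. Protocol 6.2.1.2, which describes the dosing visit, mentions extra tonometry only after injection. The permission might even be read as one repeat that follows both dilation and injection. It stands that mixing is a possibility and not an established result. The narrow reading is less natural, because the footnote covers every SRD visit and only Visit 2 has an injection. The Amendment 4 entry in Protocol section 11.4 says the option was added on investigators' feedback, but the documents do not say how often it was used.

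**The follow-up side is not known to be undilated.** This is right, and it means that the direction and size of any mixing are open. It does not answer the point, since it leaves both ends of the change undefined.

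**Little depends on it.** The analyses are descriptive, individual values are listed, and the protocol reports no apparent clinically significant IOP pattern in the SRD part. This limits the consequence to the summary tables.

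**The MD part.** A reader might infer that, without clock times, the mandatory post-injection reading could serve as the MD baseline. The documents do not support that: the parenthesis about V2 explains a definition that requires the reading to precede the first administration.

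**Redactions.** Parts of the SAP are blacked out. A selection rule there cannot be excluded, and neither can summaries of other ophthalmic variables, so no weight is placed on IOP being the only one summarised.

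**Conclusion.** The point holds in conditional form. Followed as written, SAP 6.7 makes a post-dilation reading the SRD baseline whenever one was taken and timed before the injection. In addition, the readable SAP does not say which IOP reading represents a visit. The reported SRD changes can then compare different pupil states.

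The size is d/3 or d/6 per affected patient: 0.3 to 1.7 mmHg or 0.2 to 0.8 mmHg if d is 1 to 5 mmHg. This assumes an undilated follow-up reading and a d that is constant over visits. The range for d does not come from the documents.

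It would go too far to say that the reported changes do mix pupil states, that the MD baseline is at risk, or that the primary endpoint is affected. The effect is confined to descriptive IOP change summaries in the SRD part. The plan should still be changed, because the defect lies in a stated rule and is cheap to remove.

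**What to change.** Add to SAP 6.7 and 7.8.5:

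- IOP baseline is the last pre-dilation reading before the first injection.
- The IOP value at each visit is the scheduled pre-dilation reading.
- Post-dilation and post-injection readings are shown as separate time points and are never used as baseline.

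The cost is three sentences of SAP text and a small programming change, with no new data collection. The documents do not say whether the database marks pupil state or clock time for each reading. If a reading cannot be classified, it should be listed as such and not assigned by default.

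Optionally, add for each patient and visit the study-eye minus fellow-eye difference in IOP change. Protocol 3.2 says: "A comparison between the untreated versus the treated eye is considered adequate to derive a safe and tolerable dose", while SAP 7.8.5 reports the eyes separately. This adds one derived variable. It does not replace the baseline rule, because it cancels pupil state only where both eyes were read in the same state, and the documents do not say so specifically for the optional repeats.

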## **11. HISTORY TABLE**

Table 11: 1 History table

Version	Date (DD-MMM-YY)	Author	Sections changed	Brief description of change
1	08-SEP-22		None	This is the final TSAP
